	Normal	•	•		XX	XX	XX	XX	XX	XX	XX	XX	XX
		xx (xx.x) xx (xx.x) x	x (xx.x)	(xx.x)	(xx.x)	(xx.x)	(xx.x)	(xx.x)	(xx.x)	(xx.x)	(xx.x)	(xx.)
	High	•		•	xx	XX	XX	xx	xx	XX	XX	XX	· xx
	-	xx (xx.x) xx (xx.x) x	x (xx.x)	(xx.x)	(xx.x)	(xx.x)	(xx.x)	(xx.x)	(xx.x)	(xx.x)	(xx.x)	(xx.)

^[1] Worst (most extreme) values presented for CRP. Reference: Listing xx.x.x.x

date time

Table 14.3.1.1

Overall Summary of Treatment-Emergent Adverse Events
(Safety Population)

	GLS-1027	GLS-1027	Placebo	Overall
	120 mg	360 mg	(N=XX)	(N=XX)
	(N=XX)	(N=XX)		
ubjects with any TEAE	x (xx.x%)	x (xx.x%)	x (xx.x%)	x (xx.x%)
ubjects whose strongest TEAE relationship to study drug is	x (xx.x%)	x (xx.x%)	x (xx.x%)	x (xx.x%)
ubjects whose strongest TEAE relationship to study drug is out related [2]	x (xx.x%)	x (xx.x%)	x (xx.x%)	x (xx.x%)
ubjects whose maximum TEAE severity grade is grade 1 [3]	x (xx.x%)	x (xx.x%)	x (xx.x%)	x (xx.x%)
ubjects whose maximum TEAE severity grade is grade 2 [3]	x (xx.x%)	x (xx.x%)	x (xx.x%)	x (xx.x%)
ubjects whose maximum TEAE severity grade is grade 3 [3]	x (xx.x%)	x (xx.x%)	x (xx.x%)	x (xx.x%)
ubjects whose maximum TEAE severity grade is grade 4 [3]	x (xx.x%)	x (xx.x%)	x (xx.x%)	x (xx.x%)
ubjects with any SAE	x (xx.x%)	x (xx.x%)	x (xx.x%)	x (xx.x%)
ubjects with any Serious TEAE	x (xx.x%)	x (xx.x%)	x (xx.x%)	x (xx.x%)
ubjects with any TEAE leading to study discontinuation	x (xx.x%)	x (xx.x%)	x (xx.x%)	x (xx.x%)
ubjects with any TEAE leading to death	x (xx.x%)	x (xx.x%)	x (xx.x%)	x (xx.x%)

AE = Adverse Event; SAE = Serious Adverse Event; TEAE = Treatment-Emergent Adverse Event;

^[1] Related TEAEs are those with a relationship of related, possibly related, or probably related. If the relationship is missing, it is considered related.

^[2] Not related TEAEs are those with a relationship of unlikely related or not related.

^[3] Severity grades are determined according to the NCI Common Terminology Criteria for Adverse Events version 5.0. Reference: Listing 16.2.7.1

Table 14.3.1.2

Treatment-Emergent Adverse Events by System Organ Class and Preferred Term (Safety Population)

System Organ Class	GLS-1027	GLS-1027	Placebo	Overall
Preferred Term	120 mg	360 mg	(N=XX)	(N=XX)
	(N=XX)	(N=XX)		
Subjects with at least				
one TEAE	x (xx.x%)	x (xx.x%)	x (xx.x%)	x (xx.x%)
<system #1="" class="" organ=""></system>	x (xx.x%)	x (xx.x%)	x (xx.x%)	x (xx.x%)
<preferred #1="" term=""></preferred>	x (xx.x%)	x (xx.x%)	x (xx.x%)	x (xx.x%)
<preferred #2="" term=""></preferred>	x (xx.x%)	x (xx.x%)	x (xx.x%)	x (xx.x%)
<system #2="" class="" organ=""></system>	x (xx.x%)	x (xx.x%)	x (xx.x%)	x (xx.x%)
<preferred #1="" term=""></preferred>	x (xx.x%)	x (xx.x%)	x (xx.x%)	x (xx.x%)
<preferred #2="" term=""></preferred>	x (xx.x%)	x (xx.x%)	x (xx.x%)	x (xx.x%)
•				
•				

AE=Adverse Event; TEAE = Treatment-Emergent Adverse Event; MedDRA = Medical Dictionary for Regulatory Activities.

AEs are coded using MedDRA version 23.0 and ordered by descending order of overall incidence of SOC and overall incidence of PT within each SOC. At each level of summation (overall, SOC, PT), subjects reporting more than one TEAE are counted only once.

Reference: Listing 16.2.7.1

Table 14.3.1.3

Treatment-Emergent Adverse Events by System Organ Class, Preferred Term, and Strongest Relationship to Study Drug
(Safety Population)

System Organ Class Preferred Term		-1027 0 mg	GLS-1027 360 mg		Placebo (N=XX)			erall =XX)	
	(N=XX)		(N=XX)						
	Related	Not Related	Related	Not Related	Related	Not Related	Related	Not Related	
Subjects with at least one related TEAE	x (xx.x%)	x (xx.x%)	x (xx.x%)	x (xx.x%)	x (xx.x%)	x (xx.x%)	x (xx.x%)	x (xx.x%)	
<system #1="" class="" organ=""></system>	x (xx.x%)	x (xx.x%)	x (xx.x%)	x (xx.x%)	x (xx.x%)	x (xx.x%)	x (xx.x%)	x (xx.x%)	
<preferred #1="" term=""></preferred>	x (xx.x%)	x (xx.x%)	x (xx.x%)	x (xx.x%)	x (xx.x%)	x (xx.x%)	x (xx.x%)	x (xx.x%)	
<preferred #2="" term=""></preferred>	x (xx.x%)	x (xx.x%)	x (xx.x%)	x (xx.x%)	x (xx.x%)	x (xx.x%)	x (xx.x%)	x (xx.x%)	
<system #2="" class="" organ=""></system>	x (xx.x%)	x (xx.x%)	x (xx.x%)	x (xx.x%)	x (xx.x%)	x (xx.x%)	x (xx.x%)	x (xx.x%)	
<preferred #1="" term=""></preferred>	x (xx.x%)	x (xx.x%)	x (xx.x%)	x (xx.x%)	x (xx.x%)	x (xx.x%)	x (xx.x%)	x (xx.x%)	
<preferred #2="" term=""></preferred>	x (xx.x%)	x (xx.x%)	x (xx.x%)	x (xx.x%)	x (xx.x%)	x (xx.x%)	x (xx.x%)	x (xx.x%)	
•									

AE=Adverse Event; TEAE = Treatment-Emergent Adverse Event; MedDRA = Medical Dictionary for Regulatory Activities.

AEs are coded using MedDRA version 23.0 and ordered by descending order of overall incidence of SOC and overall incidence of PT within each SOC. At each level of summation (overall, SOC, PT), subjects reporting more than one TEAE are counted only once using the strongest relationship. Related TEAEs are those with a relationship of related, possibly related, or probably related. If the relationship is missing, it is considered related. Not Related TEAEs are those with a relationship of unlikely related or not related. Reference: Listing 16.2.7.1

Page 1 of x

GeneOne Life Science Inc. Protocol: GLS27-005

Table 14.3.1.4

Treatment-Emergent Adverse Events by System Organ Class, Preferred Term, and Maximum Severity Grade
(Safety Population)

System Organ Class				
Preferred Term	Grade 1	Grade 2	Grade 3	Grade 4
Subjects with at least one TEAE	x (xx.x%)	x (xx.x%)	x (xx.x%)	x (xx.x%)
<system #1="" class="" organ=""></system>	x (xx.x%)	x (xx.x%)	x (xx.x%)	x (xx.x%)
<preferred #1="" term=""></preferred>	x (xx.x%)	x (xx.x%)	x (xx.x%)	x (xx.x%)
<preferred #2="" term=""></preferred>	x (xx.x%)	x (xx.x%)	x (xx.x%)	x (xx.x%)
<system #2="" class="" organ=""></system>	x (xx.x%)	x (xx.x%)	x (xx.x%)	x (xx.x%)
<preferred #1="" term=""></preferred>	x (xx.x%)	x (xx.x%)	x (xx.x%)	x (xx.x%)
<preferred #2="" term=""></preferred>	x (xx.x%)	x (xx.x%)	x (xx.x%)	x (xx.x%)

AE=Adverse Event; TEAE = Treatment-Emergent Adverse Event; MedDRA = Medical Dictionary for Regulatory Activities

AEs are coded using MedDRA version 23.0 and ordered by descending order of overall incidence of SOC and overall incidence of PT within each SOC.

At each level of summation (overall, SOC, PT), subjects reporting more than one TEAE are counted only once using the highest grade.

Severity grades are determined according to the NCI Common Terminology Criteria for Adverse Events version 5.0.

Reference: Listing 16.2.7.1

Repeat Table Layout for:

Table 14.3.1.5

Related Treatment-Emergent Adverse Events by System Organ Class, Preferred Term, and Maximum Severity Grade (Safety Population)

Table 14.3.2.1 Serious Adverse Events by System Organ Class and Preferred Term (Safety Population)

System Organ Class Preferred Term	GLS-1027 120 mg (N=XX)	GLS-1027 360 mg (N=XX)	Placebo (N=XX)	Overall (N=XX)
Subjects with at least one serious AE	x (xx.x%)	x (xx.x%)	x (xx.x%)	x (xx.x%)
<system #1="" class="" organ=""></system>	x (xx.x%)	x (xx.x%)	x (xx.x%)	x (xx.x%)
<preferred #1="" term=""></preferred>	x (xx.x%)	x (xx.x%)	x (xx.x%)	x (xx.x%)
<preferred #2="" term=""></preferred>	x (xx.x%)	x (xx.x%)	x (xx.x%)	x (xx.x%)
System Organ Class #2>	x (xx.x%)	x (xx.x%)	x (xx.x%)	x (xx.x%)
<pre><preferred #1="" term=""></preferred></pre>	x (xx.x%)	x (xx.x%)	x (xx.x%)	x (xx.x%)
<preferred #2="" term=""></preferred>	x (xx.x%)	x (xx.x%)	x (xx.x%)	x (xx.x%)
•				

AE=Adverse Event; Adverse Event; MedDRA = Medical Dictionary for Regulatory Activities.

AEs are coded using MedDRA v23.0 and ordered by descending order of overall incidence of SOC and overall incidence of PT within each SOC. At each level of summation (overall, SOC, PT), subjects reporting more than one AE are counted only once. Reference: Listing 16.2.7.2

date time

Table 14.3.2.2

Serious Treatment-Emergent Adverse Events by System Organ Class and Preferred Term (Safety Population)

System Organ Class Preferred Term	GLS-1027 120 mg (N=XX)	GLS-1027 360 mg (N=XX)	Placebo (N=XX)	Overall (N=XX)
Subjects with at least one serious TEAE	x (xx.x%)	x (xx.x%)	x (xx.x%)	x (xx.x%)
<system #1="" class="" organ=""></system>	x (xx.x%)	x (xx.x%)	x (xx.x%)	x (xx.x%)
<pre><preferred #1="" term=""></preferred></pre>	x (xx.x%)	x (xx.x%)	x (xx.x%)	x (xx.x%)
<preferred #2="" term=""></preferred>	x (xx.x%)	x (xx.x%)	x (xx.x%)	x (xx.x%)
:System Organ Class #2>	x (xx.x%)	x (xx.x%)	x (xx.x%)	x (xx.x%)
<pre><preferred #1="" term=""></preferred></pre>	x (xx.x%)	x (xx.x%)	x (xx.x%)	x (xx.x%)
<preferred #2="" term=""></preferred>	x (xx.x%)	x (xx.x%)	x (xx.x%)	x (xx.x%)
•	, ,		. ,	, ,

AE=Adverse Event; TEAE = Treatment-Emergent Adverse Event; MedDRA = Medical Dictionary for Regulatory Activities.

AEs are coded using MedDRA v23.0 and ordered by descending order of overall incidence of SOC and overall incidence of PT within each SOC. At each level of summation (overall, SOC, PT), subjects reporting more than one TEAE are counted only once.

Reference: Listing 16.2.7.2

Table 14.3.2.3

Treatment-Emergent Adverse Events Leading to Study Discontinuation by System Organ Class and Preferred Term
(Safety Population)

System Organ Class Preferred Term	GLS-1027 120 mg	GLS-1027 360 mg	Placebo (N=XX)	Overall (N=XX)
	(N=XX)	(N=XX)		
Subjects with at least one TEAE leading to study				
discontinuation	x (xx.x%)	x (xx.x%)	x (xx.x%)	x (xx.x%)
<system #1="" class="" organ=""></system>	x (xx.x%)	x (xx.x%)	x (xx.x%)	x (xx.x%)
<preferred #1="" term=""></preferred>	x (xx.x%)	x (xx.x%)	x (xx.x%)	x (xx.x%)
<preferred #2="" term=""></preferred>	x (xx.x%)	x (xx.x%)	x (xx.x%)	x (xx.x%)
System Organ Class #2>	x (xx.x%)	x (xx.x%)	x (xx.x%)	x (xx.x%)
<pre><preferred #1="" term=""></preferred></pre>	x (xx.x%)	x (xx.x%)	x (xx.x%)	x (xx.x%)
<preferred #2="" term=""></preferred>	x (xx.x%)	x (xx.x%)	x (xx.x%)	x (xx.x%)
•				

AE=Adverse Event; TEAE = Treatment-Emergent Adverse Event; MedDRA = Medical Dictionary for Regulatory Activities

AEs are coded using MedDRA v23.0 and ordered by descending order of overall incidence of SOC and overall incidence of PT within each SOC. At each level of summation (overall, SOC, PT), subjects reporting more than one TEAE are counted only once.

Reference: Listing 16.2.7.4

Table 14.3.2.4

Treatment-Emergent Adverse Events Leading to Death by System Organ Class and Preferred Term
(Safety Population)

System Organ Class Preferred Term	GLS-1027 120 mg (N=XX)	GLS-1027 360 mg (N=XX)	Placebo (N=XX)	Overall (N=XX)
Subjects with at least one TEAE leading to death	x (xx.x%)	x (xx.x%)	x (xx.x%)	x (xx.x%)
<system #1="" class="" organ=""></system>	x (xx.x%)	x (xx.x%)	x (xx.x%)	x (xx.x%)
<preferred #1="" term=""></preferred>	x (xx.x%)	x (xx.x%)	x (xx.x%)	x (xx.x%)
<preferred #2="" term=""></preferred>	x (xx.x%)	x (xx.x%)	x (xx.x%)	x (xx.x%)
:System Organ Class #2>	x (xx.x%)	x (xx.x%)	x (xx.x%)	x (xx.x%)
<preferred #1="" term=""></preferred>	x (xx.x%)	x (xx.x%)	x (xx.x%)	x (xx.x%)
<preferred #2="" term=""></preferred>	x (xx.x%)	x (xx.x%)	x (xx.x%)	x (xx.x%)
•				

AE = Adverse Event; TEAE = Treatment-Emergent Adverse Event; MedDRA = Medical Dictionary for Regulatory Activities

AEs are coded using MedDRA v23.0 and ordered by descending order of overall incidence of SOC and overall incidence of PT within each SOC. At each level of summation (overall, SOC, PT), subjects reporting more than one TEAE are counted only once.

Reference: Listing 16.2.7.1

Table 14.3.4.1 Hematology (Safety Population)

		GLS-	1027	GLS-	1027	Plac	cebo	To-	tal
) mg	366) mg	(N=	xx)		: xx)
Test	Time Point	(N=xx)			·xx)	`	,	•	•
		Result	Change from Baseline						
<test #1
(<unit>)</unit></test>	> Baseline								
	n	XX		xx		xx		XX	
	Mean (SD)	xx.x (xx.xx)		xx.x (xx.xx)		xx.x (xx.xx)		xx.x (xx.xx)	
	Median	xx.x		XX.X		XX.X		XX.X	
	Min, Max	XX, XX		xx, xx		xx, xx		xx, xx	
	Day 2								
	n	xx	XX	XX	XX	XX	XX	XX	XX
	Mean (SD)	xx.x (xx.xx)	xx.x (xx.xx)						
	Median	xx.x	xx.x	xx.x	XX.X	XX.X	xx.x	xx.x	xx.x
	Min, Max	XX, XX	xx, xx						
	Etc.								

Baseline is the last non-missing value prior to first dose of study treatment.

Reference: Listing 16.2.8.1

Programming Note: Continue for all hematology tests.

Repeat Table 14.3.4.1 Layout for:

Table 14.3.4.2 Chemistry (Safety Population) Protocol: GLS27-005

Table 14.3.4.3
Shift from Baseline in Hematology Results by Test
(Safety Population)

「est [1]			GLS-1027	GLS-1027									
			120 mg		360 mg			Place	bo		Overall		
	(N=XX) Baseline				(N=XX)			(N=XX)			(N=XX)		
				Baseline			Baseline			Baseline			
-	Low	Normal	High	Low	Normal	High	Low	Normal	High	Low	Normal	High	

xx (xx.x) xx (xx

xx (xx.x) xx (

xx (xx.x) xx (xx

n

Low

Normal High

Baseline is the last non-missing value prior to first dose of study treatment.

Percentages are based on n, the number of subjects with both a baseline and post-baseline result at the study day.

Shifts are based on local labs from each site.

Reference: Listing 16.2.8.1

Programming Note: Continue for all hematology tests.

Repeat Table 14.3.4.1 Layout for:

Table 14.3.4.4

Shift from Baseline in Chemistry Results by Test and Study Day (Safety Population)

^[1] Worst (most extreme) values presented for each test.

Table 14.3.4.5

Observed and Change from Baseline in Vital Sign Results by Test and Study Day
(Safety Population)

Test	0	GLS-1027 GLS-1027			Plac	ebo	0vei	0verall	
Study Day		120 mg		360 mg	(N=)	(X)	(N=	XX)	
	-	(N=XX)		(N=XX)					
	Observed	Change from Baselin	e Observed	Change from Baseline	Change from	n Baseline	Change fro	m Baseline	
<test #1=""> (units)</test>	1								
Baseline									
n	X		X		X		X		
Mean (SD)	xx.xx (xx.xxx)		xx.xx (xx.xxx)		xx.xx (xx.xxx)		xx.xx (xx.xxx)		
Median	x.xx		x.xx		x.xx		x.xx		
Min, Max	xx.x, xx.x		xx.x, xx.x		xx.x, xx.x		xx.x, xx.x		
Day 2									
'n	X	X	x	X	X	x	х	X	
Mean (SD)	xx.xx (xx.xxx)	xx.xx (xx.xxx)	xx.xx (xx.xxx)	xx.xx (xx.xxx)	xx.xx (xx.xxx)	xx.xx (xx.xxx	x) xx.xx (xx.xxx)	xx.xx (xx.xxx)	
Median	x.xx	x.xx	x.xx	x.xx	x.xx	x.xx	x.xx	x.xx	
Min, Max	xx.x, xx.x	xx.x, xx.x	xx.x, xx.x	xx.x, xx.x	xx.x, xx.x	xx.x, xx.x	xx.x, xx.x	xx.x, xx.x	
Day 3									
n	X	x	X	×	X	x	x	X	
Mean (SD)	xx.xx (xx.xxx)	xx.xx (xx.xxx)	xx.xx (xx.xxx)	xx.xx (xx.xxx)	xx.xx (xx.xxx)	xx.xx (xx.xxx	x) xx.xx (xx.xxx)	xx.xx (xx.xxx)	
Median	x.xx	x.xx	x.xx	x.xx	x.xx	x.xx	x.xx	x.xx	
Min, Max	xx.x, xx.x	xx.x, xx.x	xx.x, xx.x	xx.x, xx.x	XX.X, XX.X	xx.x, xx.x	XX.X, XX.X	xx.x, xx.x	

Baseline is the last non-missing value prior to first dose of study treatment. Reference: Listing 16.2.8.3

date time

Programming Note: Continue for all vital sign tests.

Table 14.3.4.6.1 Shift from Baseline in 12-Lead ECG Overall Interpretation by Study Day (Safety Population)

Study Day		GLS-1027	1		GLS-102			Placebo)		0verall	
		120 mg			360 mg	•		(N=XX)			(N=XX)	
		(N=XX)			(N=XX)	•		Baselin	e		Baseline	
		Baseline	!		Baseli	ne						
	Normal	Abnormal NCS	SAbnormal CS	Normal	Abnormal N	NCS Abnormal CS	Normal	Abnormal N	CSAbnormal CS	Normal	Abnormal	Abnormal
											NCS	CS
Day 2												
n		X			X			X			X	
Normal	xx											
	(xx.x)	xx (xx.x)	xx (xx.x)	xx (xx.x)	xx (xx.x	(xx.x)	xx (xx.x)) xx (xx.x)	xx (xx.x)	xx (xx.x)	xx (xx.x)	xx (xx.x)
Abnormal	xx											
NCS	(xx.x)	xx (xx.x)	xx (xx.x)	xx (xx.x)	xx (xx.x	(xx.x)	xx (xx.x)) xx (xx.x)	xx (xx.x)	xx (xx.x)	xx (xx.x)	xx (xx.x)
Abnormal	xx											
CS	(xx.x)	xx (xx.x)	xx (xx.x)	xx (xx.x)	xx (xx.x	(xx (xx.x)	xx (xx.x)) xx (xx.x)	xx (xx.x)	xx (xx.x)	xx (xx.x)	xx (xx.x)
Day 15												
n		X			X			X			x	
Normal	xx											
	(xx.x)	xx (xx.x)	xx (xx.x)	xx (xx.x)	xx (xx.x) xx (xx.x)	xx (xx.x)) xx (xx.x)	xx (xx.x)	xx (xx.x)	xx (xx.x)	xx (xx.x)
Abnormal	xx											
NCS	(xx.x)	xx (xx.x)	xx (xx.x)	xx (xx.x)	xx (xx.x	(xx.x)	xx (xx.x)) xx (xx.x)	xx (xx.x)	xx (xx.x)	xx (xx.x)	xx (xx.x)
Abnormal	XX											
CS	(xx.x)	xx (xx.x)	xx (xx.x)	xx (xx.x)	xx (xx.x	(xx.x)	xx (xx.x)) xx (xx.x)	xx (xx.x)	xx (xx.x)	xx (xx.x)	xx (xx.x)

(N)CS = (Not) Clinically Significant.

Baseline is the last non-missing value prior to first dose of study treatment.

Percentages are based on n, the number of subjects with both a baseline and post-baseline result at the study day. Reference: Listing 16.2.8.4

date time

Table 14.3.4.6.2 Summary of QTcF Interval (msec) by Study Day and Result Category (Safety Population)

Study Day Result Category	GLS-1027 120 mg (N=XX)	GLS-1027 360 mg (N=XX)	Placebo (N=XX)	Overall (N=XX)
Baseline				
n	x	X	X	x
<=450 msec (males) or <=470 msec (females)	xx (xx.x)	xx (xx.x)	xx (xx.x)	xx (xx.x)
>450 msec (males) or >470 msec (females)	xx (xx.x)	xx (xx.x)	xx (xx.x)	xx (xx.x)
Day 2				
n	X	X	X	X
<=450 msec (males) or <=470 msec (females)	xx (xx.x)	xx (xx.x)	xx (xx.x)	xx (xx.x)
>450 msec (males) or >470 msec (females)	xx (xx.x)	xx (xx.x)	xx (xx.x)	xx (xx.x)
Change from baseline <=60 msec	xx (xx.x)	xx (xx.x)	xx (xx.x)	xx (xx.x)
Change from baseline >60 msec	xx (xx.x)	xx (xx.x)	xx (xx.x)	xx (xx.x)
Day 15				
n	X	X	X	X
<=450 msec (males) or <=470 msec (females)	xx (xx.x)	xx (xx.x)	xx (xx.x)	xx (xx.x)
>450 msec (males) or >470 msec (females)	xx (xx.x)	xx (xx.x)	xx (xx.x)	xx (xx.x)
Change from baseline <=60 msec	xx (xx.x)	xx (xx.x)	xx (xx.x)	xx (xx.x)
Change from baseline >60 msec	xx (xx.x)	xx (xx.x)	xx (xx.x)	xx (xx.x)

Baseline is the last non-missing value prior to first dose of study treatment.

Percentages are based on n, the number of subjects with a baseline and post-baseline (for Week 4) result at the study day.

Reference: Listing 16.2.8.4

time date

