1. INTRODUCTION

This study will examine whether GLS-1027 is safe, tolerated and can reduce the risk treatment failure among patients admitted to hospital with confirmed Severe Acute Respiratory Syndrome coronavirus type 2 (SARS-CoV-2) infection and who require supplemental oxygen and assess if there appears to be a dose dependent response.

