2. HYPOTHESIS AND STUDY OBJECTIVES

2.1 Hypothesis

GLS-1027 will be safe, well tolerated and, for those admitted to hospital with PCR confirmed SARS-CoV-2 infection at WHO COVID-19 classification level of 3 or 4, will reduce likelihood for progression to WHO COVID-19 classification level of 6 or greater (defined as severe pneumonitis characterized by the need for intubation with mechanical ventilation, initiation of ECMO, or death) or need for salvage treatment started 72 hours after study entry with either an IL-6 monoclonal antibody or dexamethasone at a dose of $\geq 6 \text{ mg/day}$.

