8.2 Sample Size

Based on the initial data obtained to date and data in the literature ^[1], it is anticipated that approximately 50% of subjects hospitalized with PCR-positive SARS-CoV-2 infections

(WHO COVID-19 Classification level 3 or 4) will progress to WHO COVID-19 classification level of 6 or greater as defined by one or more of the following: the need for intubation or mechanical ventilation (level 6), the need for ECMO (level 7), or any cause death (level 8). The sample size estimate for this proof of concept is based on Fisher's Exact two-sided test for 2 proportions using NQuery 8 (www.statsols.com). Estimates of admitted patients requiring salvage therapy is unknown, however, the clinical data set who require intubation is a likely subset of those whose condition worsens but do not progress to respiratory compromise.

Although the interim analysis will utilize masked treatment assignments, the O'Brien Fleming group sequential sample size estimation confirms that a single interim look would retain a cumulative exit probability of 70% with a cumulative alpha =0.05 after the final analysis using the target enrollment of 132 (44 per group) to detect a reduction of those reaching the endpoint of treatment failure, which includes advancing to WHO COVID-19 Classification level \geq 6 from 50% (SOC treated) to 25% in either treatment group of SOC plus GLS-1027. Other conditions also qualify a subject as treatment failure include: need for salvage therapy with IL-6 monoclonal antibody; or institution of salvage therapy with dexamethasone (\geq 6 mg/day), withdrawing consent from the study, becoming lost to follow-up, or discontinuation of treatment for any reason other than renal function or pregnancy. This study is not powered to assess statistically significant differences between GLS-1027 doses.

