2. STUDY OBJECTIVES

2.1. Primary Objectives

The primary objectives of the study are to evaluate the following:

- Incidence of serious adverse events relative to treatment group
- Incidence of treatment failure within 28 days from enrollment

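### The safety tables never combine the two GLS-1027 doses and plan no between-group estimate for serious adverse events; an All GLS-1027 column and risk differences with confidence intervals would supply both

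*SAP*

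**What the plan says.** The protocol puts its safety question at the level of the compound. Its Introduction states: "This study will examine whether GLS-1027 is safe, tolerated and can reduce the risk treatment failure". Section 2.1 opens its hypothesis with "GLS-1027 will be safe, well tolerated and, for those admitted to hospital". The first primary objective in SAP 2.1 is "Incidence of serious adverse events relative to treatment group". Dose also matters to the design: the Introduction adds the aim to "assess if there appears to be a dose dependent response".

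The by-arm adverse event shells in SAP Appendix C (Tables 14.3.1.1 to 14.3.1.3 and 14.3.2.1 to 14.3.2.4) have four groups: 120 mg, 360 mg, placebo and Overall. The shift, vital-sign, ECG and QTcF shells (14.3.4.3 to 14.3.4.6.2) use the same four. The haematology and chemistry shells (14.3.4.1 and 14.3.4.2) call the last group Total. Tables 14.3.1.4 and 14.3.1.5 print severity grades with no arm columns, so this point does not concern them.

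The footnotes of the adverse event shells by system organ class and preferred term say that rows are "ordered by descending order of overall incidence of SOC and overall incidence of PT within each SOC". SAP 9.1.5 asks for counts and percentages by treatment. It names no combined-dose group and plans no safety test, difference or confidence interval.

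**The concern.** Allocation is 1:1:1, so the Overall group is two thirds drug and one third placebo. It describes no treatment that anyone received, yet it is the only pooled safety column and it decides which adverse events head the tables. The group that matches the hypothesis, everyone on GLS-1027, appears nowhere.

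The plan also gives no estimate of how any active group differs from placebo in SAE incidence, although that incidence is a primary objective. A reader gets separate percentages for arms of about 44 and no statement of uncertainty. A compound-level comparison would then be assembled after unblinding, with its form open to choice.

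**Working it through.** **Inputs.** Protocol 8.2 gives 132 participants, 44 per group. Two active arms make 88 on GLS-1027 against 44 on placebo. These are randomised targets; the Safety Population (SAP 6.3) is limited to treated participants and may be smaller. The documents give neither an SAE rate nor a safety precision figure, so there is no plan figure to reproduce. The event rates below are assumptions.

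**Precision of a difference from placebo.** The Wald 95% half-width is 1.96 × √[p₀(1−p₀)/n₀ + p₁(1−p₁)/n₁], where 0 is placebo and 1 is drug.

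At 20% in all arms:
- One dose v placebo: 1.96 × √[0.16 × (1/44 + 1/44)] = 0.167, or 16.7 points.
- Both doses v placebo: 1.96 × √[0.16 × (1/44 + 1/88)] = 0.145, or 14.5 points.
- Ratio: √[(1/44 + 1/88)/(1/44 + 1/44)] = √0.75 = 0.866, so about 13% narrower.

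The same formula over other assumed rates:

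| Placebo | Drug | 44 v 44 | 88 v 44 | Ratio |
|---|---|---|---|---|
| 10% | 10% | 12.5 points | 10.9 points | 0.866 |
| 30% | 30% | 19.1 points | 16.6 points | 0.866 |
| 10% | 20% | 14.8 points | 12.2 points | 0.825 |
| 20% | 30% | 18.0 points | 15.2 points | 0.846 |

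The interval is about 13% to 18% narrower across these cases.

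**Upper bound when no event is seen on drug.** The one-sided 95% bound is 1 − 0.05^(1/n):
- n = 44: 1 − 0.05^(1/44) = 6.6%.
- n = 88: 1 − 0.05^(1/88) = 3.3%.

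**What the Overall column shows.** With an assumed 20% on each dose and 5% on placebo, Overall is (20 + 20 + 5)/3 = 15%, which is neither the drug rate nor the placebo rate.

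**What a pooled-dose column can hide.** With an assumed 5% on placebo, 5% on 120 mg and 20% on 360 mg, All GLS-1027 reads (5 + 20)/2 = 12.5%. The pooled difference from placebo is 7.5 points, against 15 points for 360 mg alone.

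**The case against.** The by-dose layout fits the stated objective, which is SAE incidence by treatment group, and dose response is in the trial's title. Nothing in either document promises a pooled safety estimate, so the shells contradict nothing. Subject counts for the pooled group are the sum of two adjacent cells, and pooled means and SDs can be rebuilt from those printed; only medians cannot. The doses differ threefold, so equal safety cannot be assumed. Appendices A and B of the SAP also let table organisation change during programming. All of this stands, and it keeps the point small.

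Three stronger readings are tempting, and the documents do not support them.

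- **That the present tables make a rare harm less likely to be seen.** For an assumed 2% risk, the chance of at least one case is 1 − 0.98^44 = 59% among 44 patients and 1 − 0.98^88 = 83% among 88. But both dose columns are printed side by side, so a case in either is visible and the chance is already 83%. A pooled column detects no further event.
- **That Overall masks a drug effect.** The placebo and dose columns stand beside it, and no SAP text uses Overall to judge safety. Apart from sorting rows, it is an uninformative column.
- **That the protocol itself calls for pooling.** Protocol 8.2 says: "This study is not powered to assess statistically significant differences between GLS-1027 doses". That sentence closes a paragraph about sample size for treatment failure and does not address how safety data are grouped.

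The objection does not answer two things. First, a primary objective has no planned between-group estimate. Second, a total that includes placebo is not something the safety text requires: SAP 7.1, 7.3 and 7.4 ask for an overall group for disposition, baseline and medical history, whereas 9.1.5, 9.3 and 9.4 ask only for results by treatment.

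**Conclusion.** The point holds as a minor, inexpensive improvement. The by-arm safety shells contain no combined GLS-1027 group, and no between-group estimate is planned for SAE incidence, although the safety hypothesis concerns GLS-1027 as a whole.

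The gain is a pre-specified compound-level estimate whose 95% interval is about 13% narrower than for either dose alone when rates are equal (14.5 against 16.7 points at 20%). With no events on drug, the upper bound is 3.3% rather than 6.6%. These figures assume 44 treated patients per arm and event rates that the documents do not supply. The pooled figure summarises GLS-1027 fairly only if the two doses carry similar risk, so it belongs beside the dose-specific results and cannot replace them.

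**What to change.** In the shells of Tables 14.3.1.1 to 14.3.4.6.2 that show arms:

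1. Add an All GLS-1027 column (both doses) beside 120 mg, 360 mg and placebo. Overall or Total may stay or be dropped.
2. Order adverse event rows by All GLS-1027 incidence, and amend the footnotes to say so.
3. For any SAE and any treatment-emergent adverse event, give the risk difference from placebo with a 95% confidence interval for All GLS-1027 and for each dose. Name the interval method in SAP 9.1.5, and state that these are estimates and not tests.

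Make the change before unblinding so that the pooled view is pre-specified. The cost is a little programming: one more column, re-sorted rows and six differences with intervals (two outcomes × three contrasts). No further patients or data are needed. The statistical downside is that pooling can dilute a harm confined to one dose, which is why the dose columns and dose-specific differences stay.
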